### **SEEK Targeted Adoption, Training, Implementation Assessment**

**SEEK Adoption Survey.** This survey will capture key considerations regarding decisions whether to adopt SEEK, including perceived barriers and strengths.

**SEEK PCP Training Evaluation Form.** This online survey will be developed to evaluate PCPs' perceptions of the training approaches and solicit input as to how the training might be improved.

**SEEK PCP Questionnaire.** (PCPQ). The PCPQ, used in both SEEK RCTs, has 5 vignettes, with 7-12 statements assessing PCPs' thinking and practice with regard to addressing the targeted CM risk factors. Each vignette is followed by statements such as "I know how to motivate parents who may be resistant to suggestions" rated on a Likert scale. Items were grouped conceptually into 4 topical scales (e.g., Substance Abuse) and also cross-cutting themes (e.g., Perceived Competence). Cronbach's alphas were adequate for most scales: Depression (.76), IPV (.80), Major Stress (.80) and Substance Abuse (.58), and for most themes: Attitudes (.77), Knowledge (.55), Comfort (.68), Competence (.74) and Practice (.70).

**SEEK PCP Survey.** This 19-item measure uses a 5-point Likert scale to assess PCPs' experience implementing SEEK including their perceptions of its relevance, ease of delivery, helpfulness and training.

**Survey.** This 23-item measure uses a 5-point Likert scale to assess staff experiences with SEEK, including how they understood their roles and perceived competence in implementing SEEK.

**Rate of Screening.** EHR data on the proportion of eligible visits where screening occurred, in a given period.

**Receipt of Services.** EHR data on referrals and receipt of services by parents with positive screens.

**SEEK Parent View of Child's PCP.** Parents rate their child's PCP on this measure adapted for pediatric practice from the Patient-Doctor Interaction Scale; reliability and validity are good. The Likert scale was changed to a yes-no response. Individual scores range from 0 – 20; higher scores indicate greater satisfaction.

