## **Measuring Costs**

The cost analysis will provide estimates of the overall practice-level costs associated with implementing SEEK. Cost measurement will be organized using the Cost of Implementing New Strategies (COINS) framework which provides a structure for measuring and categorizing costs. Implementation costs include all resources used to deliver SEEK. COINS maps onto the SIC, by tracking the costs and resources needed to complete each implementation activity. In SEEK II, PCPs in the intervention arm did not require more time per child than did controls. It seems reasonable to apply this to the current study, rather than conduct another time study.

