**Aim 1. Compare alternative approaches to implementation of SEEK with respect to clinical and implementation outcomes.** To address aim 1a, we will compare practices randomized to MOC to practices randomized to IND with respect to clinical and implementation outcomes. These include perceptions of the training from the PCPs' evaluations, scales from the SEEK PCPQ (e.g., Competence in addressing problems) and the PCP Survey (e.g., Ease of Delivery. We will also compare the groups with respect to rates of screening and parents' receipt of services and satisfaction with the PCP. For quantitative outcomes, statistical inference will be based on linear regression models; for binary outcomes, inference will be based on logistic regression models, accounting for repeated measures within PCP and system. For example, for PCPs reported Competence we will fit this model:  $E(\text{Competence}_{ijkl}) = \beta_0 + s_i + p_j + i_k + \beta_1(\text{POST}) + \beta_2(\text{POST})(\text{MOC-4})$  where Competenceijkl stands for the competence score measured at the lth time point (l=1 or 2 for baseline or follow-up respectively) of the kth PCP in the jth practice of the ith system, and  $s_i$ ,  $p_j$ ,  $i_k$  are random effects for system, practice and PCP respectively; POST=1 if it is a post-training measure and 0 otherwise, MOC = 1 if the PCP was trained using MOC and 0 if IND, and  $\beta$ 's are parameters to be estimated. Note this model assumes that the mean baseline scores are the same in both groups, as recommended for randomized studies. This model can be fitted using restricted maximum likelihood. To avoid possible biases due to selective attrition from the training, the primary analysis will follow the "intention to treat" principle including all those randomized. Secondary analyses will be based on groups defined by training received. To address Aim 1b we will compare practices who choose SEEK-online to practices who choose the traditional approach using the same statistical methods as described for Aim 1a. Outcomes of interest will include staff satisfaction, costs, rates of screening, receipt of services, and parental satisfaction.

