**Table 4. Power Calculations**

Aim	Respondents/Source	Measure	N per group	Detectable Effects with 80% power
1a	PCPs	Changes in Comfort and Competence in addressing CM	137	Effect size  of 0.42
1a	Parents	Parent satisfaction	144	Effect size  of 0.41
1b	Staff	Staff Perceptions	24/72 	Effect size  of 0.82
2	Practices	Proportion adopting	59	Precision of +/- 15 pct points
3	EHR	Pre-post prevalence of CM-related diagnoses	98,000	5% vs. 4.5%  10% vs. 9.6%

Defined as the difference in means between groups divided by the standard deviation.

Conservatively assuming an imbalance between SEEKonline vs. Traditional of as much as 25% to 75%.

In our previous evaluations of SEEK, we observed rates of CM in the medical record ranging from 5% to 1%.

methods.

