**Qualitative/Mixed Methods Analysis.** An audit trail of data collected and memos, team meetings indicating time, place, source of data, and persons collecting or analyzing information, will be kept. Procedures for data collection and the role of the investigator collecting the data will be detailed and reviewed with each member of the research team. We will analyze interview transcripts using a thematic content analysis methodology. First, transcripts will be distributed among investigators. Each will review these to develop a broad understanding of content related to the project's aims and to identify topics for discussion and observation. During this and subsequent steps, investigators will prepare short descriptive statements or "memos" to document initial impressions of topics and themes and their relationships, and to define the boundaries of specific codes (i.e., the inclusion and exclusion criteria for assigning a specific code). Second, transcripts will be independently coded to condense the data into analyzable units. Segments of text ranging from a phrase to several paragraphs will be assigned codes based on a priori (i.e., from the interview guide) or emergent themes (or, open coding). Codes will be assigned to describe connections between categories and between categories and subcategories (i.e., axial coding). Codes will also be assigned to reflect the social and demographic characteristics of study participants. Lists of codes developed by each investigator will be matched and integrated into a single codebook. Third, each text will be independently coded by at least two investigators. Disagreements in assignment or description of codes will be resolved through discussion

**Cost Analysis.** We will conduct cost effectiveness analyses taking the perspective of a practice. Total practice cost of implementation will be calculated for both training arms (IND and MOC). Cost effectiveness ratios will be calculated as the cost per average SIC component completed, and per average Competence scale and Practice Behavior scale scores. Standard time discounting methods will be applied to cost estimates. We will use sensitivity analyses to derive upper and lower estimates of resource use and intervention costs. Standard errors for use in mean comparisons will be estimated, using bootstrapping

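### The planned cost-effectiveness ratios are within-arm averages and do not give the added cost per added unit of benefit of MOC over IND

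*Combined protocol and SAP*

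**What the plan says.** The Cost Analysis paragraph of the Data Analysis Plan (printed after Table 4) names the type of analysis: "We will conduct cost effectiveness analyses taking the perspective of a practice". It totals implementation cost for each of the two training arms and then defines the measure: "Cost effectiveness ratios will be calculated as the cost per average SIC component completed, and per average Competence scale and Practice Behavior scale scores". Discounting and upper and lower bounds on resource use and cost follow. On uncertainty it says: "Standard errors for use in mean comparisons will be estimated, using bootstrapping".

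The Measuring Costs section sets the scope of the numerator: "Implementation costs include all resources used to deliver SEEK". It also links the cost instrument (COINS) to the SIC, activity by activity.

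The effect side is handled elsewhere. Under Aim 1, the Data Analysis Plan gives a mixed model for Competence with a POST x MOC term, coded "MOC = 1 if the PCP was trained using MOC and 0 if IND". The coefficient of that term is the MOC-IND effect. Nothing ties it to cost. Costs are listed as an outcome only under Aim 1b, which compares SEEKonline with the Traditional approach; practices choose between these and are not randomized to them. SIC measures are modelled under Aim 2 against practice characteristics, and the Aim 1a outcome list does not name them.

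Nowhere in the supplied text is a MOC-IND cost difference paired with a MOC-IND effect difference.

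**The concern.** Practices are randomized to MOC or IND, and the economic analysis is done for a practice. Table 1 shows that the arms share the videos, the post-test and three consultations; MOC adds four webinars and a QI project. The economic question that the randomization can answer is what the extra effort buys: added cost per added unit of benefit. Dividing an arm's whole cost by its average outcome answers a different question.

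Three things enter the average ratio that have nothing to do with the difference between the arms:

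- **Shared cost.** All resources count, so the numerator includes whatever both arms spend.
- **Competence present at baseline.** PCPs complete the PCPQ before training (Pre-implementation Phase). If the denominator is a mean level, training cost is credited with competence that was already there.
- **The zero point of the scale.** PCPQ items are "rated on a Likert scale" and the coding is not stated. A ratio to a mean level changes when the same items are coded from 0 instead of 1.

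The last two depend on how the scores are taken. The Cost Analysis paragraph speaks of average scores, while Table 4 labels the same outcome "Changes in Comfort and Competence in addressing CM". With changes from baseline, both disappear. The shared cost remains either way.

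**Working it through.** The documents state no cost-effectiveness figure for this trial, so there is none to reproduce. Everything below is illustration; assumed inputs are marked.

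**1. Known training increment.** Table 1 gives 2.5 h of videos (the text on training says 2-3 h for IND), 3 h of consultations in both arms, and 4 h of webinars in MOC only.
- Common training time: 2.5 + 3 = 5.5 h per PCP (5 to 6 h over the 2-3 h range).
- MOC minus IND: 4 h per PCP, plus QI-project time, which is not given.

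**2. Incremental figure for Competence.** Table 4 gives a detectable effect of 0.42 SD with 137 PCPs per group and a 1.5-fold variance increase.
- Check: (1.960 + 0.842) x sqrt(2 x 1.5/137) = 2.802 x 0.148 = 0.415, in line with 0.42.
- At that effect: 4/0.42 = 9.5 h per SD. QI time would raise it, so it is a floor at that effect size.
- Implied SE: 0.42/2.802 = 0.150. The 95% limits of an observed 0.42 are 0.42 +/- 0.294 = 0.126 to 0.714 SD.
- Over those limits the webinar hours alone give 4/0.714 = 5.6 to 4/0.126 = 31.7 h per SD. Hours are held fixed and QI time is left out, so this is not an interval for the real ratio.
- None of these figures depends on the shared cost.

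**3. Average against incremental ratio for SIC.** The SIC has 45 activities. Assume 30 completed in IND and 30 + d in MOC. Let S be all cost common to both arms, in hours per PCP.
- MOC average = (S + 4)/(30 + d)
- Incremental = 4/d
- Incremental divided by MOC average = 4(30 + d)/[d(S + 4)]

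With S = 5.5 h of training plus an assumed 0, 10 or 20 h of other shared cost:

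| Other shared cost | d = 3 | d = 6 | d = 9 |
|---|---|---|---|
| 0 h (S = 5.5) | 4.63 | 2.53 | 1.82 |
| 10 h (S = 15.5) | 2.26 | 1.23 | 0.89 |
| 20 h (S = 25.5) | 1.49 | 0.81 | 0.59 |

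For d = 6 the MOC average is 9.5/36 = 0.26, 19.5/36 = 0.54 and 29.5/36 = 0.82 h per activity, while the incremental figure stays at 4/6 = 0.67. The two are equal when S = 120/d, that is 40, 20 or 13.3 h for d = 3, 6, 9. With about 275/48 = 5.7 PCPs per practice, all the ratios scale alike and the multiples do not change.

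**4. Zero point, only if mean levels are used.** Assume means of 3.5 (IND) and 4.1 (MOC) on 1-5 coding. Coding the items 0-4 turns these into 2.5 and 3.1.
- The IND ratio rises by 3.5/2.5 - 1 = 40%; the MOC ratio by 4.1/3.1 - 1 = 32%.
- The difference is 0.6 under both codings, so the incremental ratio does not change.

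**5. Why separate standard errors are not enough.** For R = dC/dE, where dC and dE are the cost and effect differences, the approximate variance is R² x [Var(dC)/dC² + Var(dE)/dE² - 2 Cov(dC, dE)/(dC x dE)]. Separate standard errors give the first two terms. The covariance has to come from resampling cost and effect together.

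**The case against.** **Cost per SIC component is a legitimate quantity.** COINS tracks resources by SIC activity, so this ratio is that instrument's natural unit cost. The stated economic purpose is largely affordability to a practice, and Aim 2 asks about each strategy. This stands: the ratio should stay as a descriptive result. A reader might infer that the planned ratios are wrong and should be removed; the documents do not support that.

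**The incremental figure is one subtraction and one division away.** For Competence this is true of the point estimate: per-arm costs and the POST x MOC effect are both planned. A reader might infer that the plan cannot produce an incremental figure or compares nothing between arms. That goes too far, since Aim 1a estimates the effect and comparisons of means with bootstrap standard errors are foreseen. What remains is that the pairing is not planned, its joint uncertainty is not available, and no MOC-IND contrast is specified for SIC activities.

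**The illustration rests on assumed inputs and lands on both sides of 1.** Correct. It shows that the two quantities differ, not by how much here. A reader might infer that the average ratios flatter MOC, or that recoding would reverse the arms' order. Neither follows: the direction depends on the shared cost and the order on the cost ratio, and the documents give neither.

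**A cost per SD of self-rated competence has no decision rule.** Also true, since no value per unit is given. That argues against requiring an acceptability curve. The added cost and added effect can still be reported side by side.

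**Conclusion.** The point holds in this form: the stated ratios are costs over averages, and they do not give the added cost per added unit of benefit of MOC over IND. The reading that the ratios are formed within arm comes from the order of two adjacent sentences and is the natural one.

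The size cannot be stated for this trial. The only increment the documents quantify is 4 webinar hours per PCP, which makes 9.5 h per SD a floor at an effect of 0.42 SD. Under the assumed SIC counts, the incremental ratio runs from 0.59 to 4.6 times MOC's average ratio. The points about baseline competence and item coding apply only if mean levels, not changes, are used.

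The change is worth making because the stated method leaves the randomized economic comparison unanswered and the remedy uses data already planned. A reader might take this as a threat to the trial's main conclusions. It is not: the cost analysis is secondary, and the Aim 1 and Aim 3 inferences do not use it.

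**What to change.** Keep the per-arm costs and the cost per SIC activity as descriptive results. Add, as the MOC-IND cost-effectiveness measure, the difference in mean practice cost paired with the difference in effect:

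- for Competence, the POST x MOC contrast already specified under Aim 1;
- for Practice Behavior, the same model;
- for SIC, an added MOC-IND contrast in activities completed.

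Bootstrap cost and effect jointly by resampling practices within arm and practice type, with healthcare system kept in the effect model or in the resampling. Show the result on a cost-effectiveness plane. An acceptability curve is optional. State whether scale scores are follow-up means or changes from baseline, and how items are coded.

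The cost is a few sentences of plan text and a little more analysis on the same data: one added contrast, and a refit of the effect model in each bootstrap replicate. Intervals will be wide with about 48/2 = 24 practices per arm, of which 13/2 = 6 or 7 are pediatric. The ratio is unstable if the effect difference is near zero, which is the reason for the plane.

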### **Implementation Process and Outcomes**

The **Stages of Implementation Completion (SIC)** is an observational assessment tool developed in a large randomized implementation trial. The SIC has 8 stages, each including sub-activities, extending from Engagement with the developers to achievement of practitioner Competency. Each stage maps onto 3 phases of implementation (Pre-Implementation, Implementation and Sustainment). Competency is viewed as *entering* into the Sustainment phase. Sustainment is an ongoing process toward achievement of Stage 8.

The SIC has been adapted for over 20 different implementation strategies involving varied interventions. These multiple adaptations led to the development of the empirically derived *Universal SIC*, with items found to be relevant and reliably utilized across each of the adaptations, regardless of service sector or population (e.g., child welfare, primary care, prevention). The Universal SIC spans the 8 original SIC stages, with 45 activities tracked during implementation. For the current study, completion of activities will be monitored by the practice manager and collected monthly by the research team, with data entered into the SIC data collection website. The website is managed by the SIC team, and through a web-based tool, implementation performance at the practice level can be benched against other implementation efforts.

**SIC Scores.** Three scores are calculated for each SIC stage. First, the time that a practice takes for a stage is calculated (Duration Score). Because the implementation process is nonlinear, the Duration Score takes into account activities that may not be completed sequentially within a stage. If a site completes only one activity in

a stage, the Duration Score for that stage is a single day. Duration Scores are calculated separately for each stage due to the potential for overlap across stages; the total Duration Score does not necessarily equal the summation of each stage's Duration. Rather, the total Duration Score is calculated from the date of the first completed SIC activity to the final activity completed, regardless of the stage in which it occurred. Second, the percentage of activities completed within a stage is calculated Proportion Score). Similar to Duration,

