**Aim 2. Examine variations in SEEK's implementation process and impacts and understand associated barriers and facilitators in pediatric and family medicine practices.** We will determine the proportion of practices that agree to adopt SEEK. We will then quantitatively assess the relationship between practice characteristics (e.g., demographics, EBP attitudes) and willingness to adopt SEEK. The most important independent predictors will be determined using multivariable logistic regression models. Among those that do adopt SEEK, we will assess their degree of completeness, speed, and quality of implementation using the SIC. Completeness will be summarized using the final stage attained (0-8). Speed will be summarized by the duration in each stage, and quality by the proportion of activities performed at each stage, and overall. The distribution of these variables will be determined, overall and separately, based on the type of

practice. The distribution of time to achieve each phase will be estimated using the Kaplan-Meier approach. Barriers and facilitators to implementing SEEK will be probed quantitatively and qualitatively (see below). Among practices adopting SEEK, we will examine the association between practice characteristics and measures of completeness, speed, and quality of implementation from the SIC. We will examine relationships between practice characteristics and implementation by comparing the distribution of SIC scores in groups defined by practice characteristics. Finally, the most important predictors of degree of implementation will be determined using multivariable regression models with practice characteristics as predictors and SIC measures as outcomes. In addition to studying implementation at the practice level, we will analyze the relationship between PCP level measures of implementation (e.g., screening rates) and PCP characteristics, facilitators and barriers. These models will account for clustering of PCPs within practices, as described above.

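### Cost per SIC component is an average unit cost partly tied to its own denominator, and no incremental MOC-versus-IND ratio is stated, so it cannot rank the two trainings on value

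*Combined protocol and SAP*

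**What the plan says.** The Cost Analysis paragraph takes the practice's perspective and computes total implementation cost in each training arm. It then says: "Cost effectiveness ratios will be calculated as the cost per average SIC component completed", "and per average Competence scale and Practice Behavior scale scores". It adds discounting, sensitivity analyses on resource use, and bootstrap standard errors for comparing means. It states no difference in cost over difference in effect, no dominance rule and no net-benefit measure, and it does not name the unit to be resampled.

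The Measuring Costs section explains the numerator: "COINS maps onto the SIC, by tracking the costs and resources needed to complete each implementation activity". It also sets a wider scope: "Implementation costs include all resources used to deliver SEEK".

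The Implementation Process and Outcomes section gives the size of the instrument: "The Universal SIC spans the 8 original SIC stages, with 45 activities tracked during implementation". The plan does not say whether a component, in the ratio, means an activity or a stage.

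**The concern.** A cost-effectiveness ratio is meant to show what is gained for what is spent. Here the gain is completion of SIC activities, and the spending is recorded largely by tracking what those activities consume. An arm that leaves activities undone tends to have both a lower cost and a lower count. The quotient then describes the average price of what was done and says little about how much was done.

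The economic comparison is a stated part of Aim 2, and the Training section expects MOC to give the more efficient adoption. If this ratio is read as evidence of value, its ranking of MOC and IND could reflect which activities happen to be expensive, whichever training achieved more implementation.

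**Working it through.** The documents give no cost, ratio or completion count by arm, so there is no planned figure to reproduce. The check asks how the stated ratio behaves.

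**Inputs.** From the protocol: 45 activities, and MOC has four one-hour webinars and a QI project that IND lacks (Table 1). Assumed for illustration: 20 early and 25 later activities, prices of $100 and $400, and a stalled arm that completes the 20 early and 5 later ones. A component is read as an activity.

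**Formulas.** Average ratio = total cost / activities completed. Incremental ratio = (cost of complete arm − cost of stalled arm) / (45 − 25).

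1. *Equal prices, $100 each.* Stalled: 2,500/25 = $100. Complete: 4,500/45 = $100. The ratio does not register the 20 missing activities.

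2. *Later steps dearer (early $100, later $400).* Stalled: (20×100 + 5×400)/25 = 4,000/25 = $160. Complete: (20×100 + 25×400)/45 = 12,000/45 = $267. The stalled arm looks 40% cheaper (160/266.7 = 0.60).

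3. *Early steps dearer (early $400, later $100).* Stalled: (20×400 + 5×100)/25 = 8,500/25 = $340. Complete: (20×400 + 25×100)/45 = 10,500/45 = $233. The complete arm now looks better.

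4. *A common cost F outside the listed activities, with the prices of step 2.* Setting (4,000+F)/25 = (12,000+F)/45 gives 180,000 + 45F = 300,000 + 25F, so F = $6,000. Below this the stalled arm looks better, and above it the complete arm does.

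5. *Extra MOC training cost T outside the listed activities, equal prices of $100, MOC complete and IND stalled.* MOC is (4,500+T)/45. For T = 500, 1,000 and 2,000 this is $111.1, $122.2 and $144.4, against $100 for IND. MOC looks worse although it completed everything.

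6. *Incremental ratio.* Step 2: 8,000/20 = $400. Step 3: 2,000/20 = $100. Step 5 with T = 1,000: (5,500 − 2,500)/20 = $150. The last figure exceeds the $100 activity price because it includes what MOC adds. Reported beside the completion counts, an incremental ratio keeps the 20-activity difference in view.

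**The case against.** The strongest reply has four parts.

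First, the numerator may be more than the sum of listed activities, because the Measuring Costs section counts all resources used to deliver SEEK. This stands. A reader might infer that the ratio is a pure tautology, with the same steps above and below the line. The documents support only partial coupling.

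Second, the direction is open. A reader might infer that the ratio rewards the arm that stalls. Steps 3 and 4 show that it can equally favour the complete arm. The Procedures section has training and the EHR connection finished by month 8 in cohort 1, before delivery begins in month 9, and the plan carries over the SEEK II finding of no extra PCP time per child. Neither fact suggests sharply rising costs, but neither establishes a profile.

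Third, a reader might infer that an incremental SIC ratio would be just as empty, giving only the price of the extra steps. That follows only if shared steps cost the same in both arms and MOC adds nothing outside them. Table 1 shows that MOC has added inputs, so the incremental ratio can carry information about value.

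Fourth, a shortfall would be visible elsewhere. Total cost is calculated by arm, the Aim 2 analysis reports SIC stage, duration and proportion, and the Aim 1 analysis compares screening rates. The Competence and Practice Behavior ratios are not built from SIC activities, and no powered comparison rests on the SIC ratio. This limits the harm. It does not make the stated ratio suitable for comparing the arms, and the two scale ratios are also averages with no incremental form.

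**Conclusion.** The point holds in a limited form. Cost per SIC component is an average unit cost whose numerator is partly driven by its denominator, and the plan states no incremental comparison of MOC with IND. At equal prices the ratio is insensitive to completion. At unequal prices it can point either way: $160 against $267 or $340 against $233 for stalled against complete, depending only on which assumed price is attached to the early steps. These dollar figures are illustrations, since the documents give no cost profile. They also assume that a component is one of the 45 activities. If it means a stage, the figures do not carry over but the reasoning does.

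SIC completion remains a legitimate implementation outcome. The fault lies in dividing cost by it and calling the average a cost-effectiveness ratio. The analysis is secondary, and the change is worth making because it is cheap and bears on a comparison that Aim 2 promises.

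**What to change.** Revise the Cost Analysis paragraph as follows.

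- Define component as an activity or a stage, and label cost per SIC component a descriptive unit cost.
- Show total practice cost and SIC activities or stages completed side by side for each arm.
- Base the cost-effectiveness comparison on incremental ratios: MOC minus IND cost over MOC minus IND effect, with bootstrap intervals that resample whole practices, the unit randomized under Design.
- Use as effects the additional eligible visits screened, from the measure already defined as "EHR data on the proportion of eligible visits where screening occurred, in a given period", together with the Competence and Practice Behavior scales.
- Give the incremental SIC ratio as a supplement.

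The cost is wording and analysis code, because Table 3 already schedules the screening data from the EHR. Two limitations should be stated. Screening rates depend on EHR documentation, which is automated under SEEKonline and manual under Traditional, and practices choose between these. Screening may also use some of the resources counted as cost, so that effect is not wholly free of coupling either.
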